## Protocol Amendment History

Version      Date    Revision Summary

1.0    2024-09-07    Initial Draft

2.0    2024-11-16    Revision 1

---

## Protocol Synopsis

Item	Details
Study Title	18F-Octreotide PET/CT or PET/MR for Diagnosis, Therapeutic Response, and Prognosis in Neuroendocrine Neoplasms

Item	Details
Design	Prospective, single-center, cross-sectional study
Centers	1
Sample Size	152
Indication	Patients with suspected/confirmed NEN
Objective	Evaluate diagnostic efficacy, therapeutic response assessment, and prognostic prediction of 18F-Octreotide PET/CT or PET/MR using pathology as the gold standard.
Primary Endpoint	Completion of multimodal imaging + pathological confirmation
Inclusion Criteria	1. Clinical diagnosis of neuroendocrine neoplasms; 2. Suspected of neuroendocrine neoplasms
Exclusion Criteria	1. Inability to undergo biopsy/surgery. 2. Active malignancy/history within 5 years. 3. Severe uncontrolled comorbidities/active infection. 4. Unable to provide informed consent.
Termination Criteria	1. Study objectives met. 2. Occurrence of SAEs.
18F-Octreotide QC	Produced per Chinese Pharmacopoeia ; passed rodent safety studies; facility holds Type IV Radioactive Pharmaceutical License.
Follow-up Plan	Internal patients: Data extracted from electronic medical records. External patients: Telephone follow-up for pathological results.
Analysis Plan	SPSS 17.0 for: - Sensitivity/specificity/NPV/PPV (2x2 tables) - AUC/optimal SUV cutoff (ROC curves) - Kappa test (imaging vs. pathology concordance) - Significance: p<0.05

Item	Details
Quality Management	AE surveillance system; anonymized data storage; regulatory audit compliance; no identifiable data in publications.

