### 5. Overall Design

#### 5.1 Research Methodology

This prospective, single-center, cross-sectional study evaluates the diagnostic efficacy of 18F-Octreotide PET/CT in patients with neuroendocrine neoplasms (NEN). A total of 152 subjects will be enrolled from the First Affiliated Hospital, Zhejiang University School of Medicine.

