### 5.4 Study Endpoints:

Study completion is defined as completion of multimodal imaging and acquisition of pathological results.

---

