## 7 Statistical Considerations

### 7.1 Total Sample Size

Assuming a sensitivity of 0.90, specificity of 0.88, and disease prevalence of 0.25 from literature, with a margin of error of 0.1 and  $\alpha = 0.05$ :

For sensitivity calculation:

$$( N_1 = \frac{1.96^2 \times 0.9 \times (1-0.9)}{0.1^2 \times 0.25} = 138 )$$

For specificity calculation:

$$( N_2 = \frac{1.96^2 \times 0.88 \times (1-0.88)}{0.1^2 \times (1-0.25)} = 54 )$$

The theoretical sample size is estimated at 138 cases. Accounting for a 10% expected dropout rate (based on prior studies), the adjusted total sample size is 152 cases.

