### 7.3 Statistical Methods

Analysis performed using SPSS 17.0:

Sensitivity, specificity, and positive/negative predictive values calculated via  $2 \times 2$  contingency tables.

ROC curves used to determine AUC and optimal cut-off values (e.g., SUV thresholds).

Kappa test evaluated consistency between 18F-Octreotide PET/CT and pathological diagnoses.

Statistical significance:  $p < 0.05$ .

---

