## 9 Expected Timeline

Recruitment period: 36 months

Follow-up: Ends upon completion of 18F-Octreotide PET/CT and pathological confirmation.

---

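### The synopsis gives study completion as the primary endpoint of a diagnostic-accuracy study, and section 7.2 states a power of 0.95 that the sample size in 7.1 does not derive

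*Protocol*

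**What the plan says.** **Endpoint.** The Primary Endpoint row of the Protocol Synopsis reads "Completion of multimodal imaging + pathological confirmation". Section 5.4, headed Study Endpoints, contains one sentence: "Study completion is defined as completion of multimodal imaging and acquisition of pathological results". Section 9 says of follow-up that it "Ends upon completion of 18F-Octreotide PET/CT and pathological confirmation".

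**Purpose and analysis.** The synopsis objective is to "Evaluate diagnostic efficacy, therapeutic response assessment, and prognostic prediction of 18F-Octreotide PET/CT or PET/MR using pathology as the gold standard". Section 5.1 describes a "cross-sectional study evaluates the diagnostic efficacy of 18F-Octreotide PET/CT". Section 7.3 has "Sensitivity, specificity, and positive/negative predictive values calculated via" two-by-two tables, then ROC analysis and kappa. Section 2.2 (1)(a) lists similar accuracy measures as things to calculate, without ranking them or calling any of them an endpoint.

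**Sample size and power.** Section 7.1 assumes sensitivity 0.90 and specificity 0.88, with "disease prevalence of 0.25 from literature, with a margin of error of 0.1" and alpha 0.05. It obtains 138 for sensitivity and 54 for specificity, takes the larger, and adds 10% for dropout to reach 152. Section 7.2 then lists alpha 0.05 and a power of 0.95, with no test, null value or effect attached.

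**The concern.** A primary endpoint should be the outcome that answers the main question. Having been scanned and having a pathology result is a procedural status: a tracer with poor sensitivity meets it as readily as one with excellent sensitivity. Because the primary field holds a non-outcome and several accuracy measures are listed without rank elsewhere, nothing ties the sponsor to the measures that sized the study. Any of them could be presented as the main result once the data are known.

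The power figure raises a second problem. Power is the probability that a stated test rejects a stated null under a stated alternative. Section 7.1 offers no test and no null, so a power of 0.95 cannot come from it. A reader of 7.2 could take 152 patients to give 95% power for a test of accuracy, when the calculation supports only an expected confidence interval width.

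**Working it through.** **1. Inputs (section 7.1).** Sensitivity 0.90, specificity 0.88, prevalence 0.25, margin of error 0.1, multiplier 1.96, dropout 10%.

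**2. The plan's own figures.** The formula is N = 1.96² × p(1 − p) / (0.1² × share of patients with the relevant disease status).

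- Sensitivity: 1.96² × 0.9 × 0.1 / (0.01 × 0.25) = 138.3 (stated 138).
- Specificity: 1.96² × 0.88 × 0.12 / (0.01 × 0.75) = 54.1 (stated 54).
- Dropout: 138 × 1.10 = 151.8 (stated 152).

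All three reproduce. Alpha enters only through 1.96, the 95% confidence multiplier. No null value and no power term are used.

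**3. Could 0.95 have entered the formula?** Adding a power term in the usual way replaces 1.96² by (1.96 + 1.645)². That gives about 468 for sensitivity and 183 for specificity before dropout, not 138 and 54.

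**4. What 152 delivers under the plan's assumptions.**

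- Evaluable: 152 × 0.90 = 136.8.
- With NEN: 136.8 × 0.25 = 34.2. Without NEN: 136.8 × 0.75 = 102.6.
- Sensitivity half-width: 1.96 × √(0.9 × 0.1 / 34) = 0.101; with 35 patients, 0.099.
- Specificity half-width: 1.96 × √(0.88 × 0.12 / 103) = 0.063.

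**5. Illustration of power.** The protocol gives no null, so the null values here are assumptions. The test is an exact binomial at one-sided 0.025.

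| Measure | Patients | True value | Assumed null | Power |
|---|---|---|---|---|
| Sensitivity | 34 | 0.90 | 0.80 | 0.33 |
| Sensitivity | 34 | 0.90 | 0.75 | 0.55 |
| Sensitivity | 34 | 0.90 | 0.70 | 0.75 |
| Sensitivity | 34 | 0.90 | 0.65 | 0.95 |
| Specificity | 103 | 0.88 | 0.80 | 0.53 |
| Specificity | 103 | 0.88 | 0.75 | 0.89 |
| Specificity | 103 | 0.88 | 0.73 | 0.96 |

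The power depends wholly on the null chosen. For sensitivity it reaches 0.95 only against a null of about 0.65.

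**6. What 95% power would take, for one assumed null.** For sensitivity 0.90 against 0.80 (normal approximation): ((1.96 × √0.16 + 1.645 × √0.09) / 0.10)² = about 163 patients with NEN. At prevalence 0.25 that is 163.2 / 0.25 = about 653 evaluable patients.

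**7. The endpoint passages side by side.** The synopsis, 5.4 and 9 describe essentially one event and call it the primary endpoint, study completion and the end of follow-up respectively. The last two labels fit that event. The first does not fit the objective, 5.1, 7.1 or 7.3.

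**The case against.** The strongest reply is that this is a labelling slip. Section 2.2 (1)(a), the synopsis analysis row and section 7.3 all list accuracy measures, and the study is sized on sensitivity and specificity, so the intent is plain. The power figure feeds into no other number: 138 and 152 stand without it, and 7.1, directly above, says openly that it works from a margin of error. Section 7.3 also includes ROC analysis and kappa, which have conventional null values, so the 0.95 is underived rather than shown to be false. Finally, the illustrative powers rest on nulls that the protocol never states, and exact power at this size is jagged: against 0.80 it is 0.33 with 34 patients, 0.31 with 35 and 0.25 with 38.

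Part of this stands. The sample-size arithmetic is not in dispute, the intent can be guessed, and the illustrative powers should not be read as showing that a planned test is underpowered, because no such test is planned. But a list of unranked measures does not designate a primary endpoint, least of all when the field for it is filled with something else. Nothing in the protocol is sized for AUC or kappa, so they do not support the stated power. Nor is this detail left to a statistical analysis plan: the protocol states both items itself, and states them wrongly.

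**Conclusion.** Both parts hold. The event in the primary-endpoint field is the one that section 5.4 defines as study completion, and no accuracy measure is named as an endpoint anywhere in the protocol. The power of 0.95 is not derived from 7.1 and, without a null, is undefined for sensitivity and specificity, the two measures on which the sample size was calculated.

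What 152 patients support is precision: an expected 95% half-width of about 0.10 for sensitivity and about 0.06 for specificity. This rests on the plan's assumed accuracy, prevalence of 0.25 and 10% loss, and on the normal approximation used in 7.1. The patient counts move with the prevalence actually enrolled, which matters because section 5.3.1 admits patients with a clinical diagnosis as well as those under suspicion. The defects lie in what the study is declared to show; they do not by themselves require a different sample size.

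**What to change.** - **Synopsis and 5.4:** name sensitivity and specificity of 18F-Octreotide PET against pathology, each with a 95% confidence interval, as the primary endpoints. Sensitivity would continue to drive the sample size, as it already does in 7.1 (138 against 54). State that the unit is the patient, which is what the prevalence-based formula counts. Keep the completion event only as the study-completion definition.
- **7.2:** delete the power of 0.95. State that 152 is precision-based, with an expected 95% half-width of about 0.10 for sensitivity (about 34 to 35 patients with NEN) and about 0.06 for specificity (about 103 without), under the plan's assumptions.
- **If a hypothesis test is wanted instead:** state the null values and report the power that 152 actually gives.

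The first two changes are a wording amendment with no added enrolment; the only loss is the 95% power claim. Keeping 95% power for a test would change the sample size. Against an assumed null sensitivity of 0.80, for instance, it would need about 653 evaluable patients.

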## Abbreviations

Abbreviation	Full Term
PET	Positron Emission Tomography
CT	Computed Tomography
ROC	Receiver Operating Characteristic Curve
SSTR	Somatostatin Receptors

## 1. Research Background

Neuroendocrine neoplasms (NEN) are heterogeneous tumors. Neuroendocrine cells are distributed throughout multiple organs and tissues, enabling NEN to arise in various sites, commonly the gastrointestinal tract, pancreas, and lungs. Symptoms may relate to hormone secretion and bioactive peptides entering systemic circulation [1]. Beyond these sites, NEN can also occur in other endocrine organs (e.g., thymus, adrenal glands, pituitary, thyroid, and parathyroid). Over the past decade, NEN incidence and prevalence have increased [2]. Amidst the rise of precision oncology, solid tumor treatment has entered an era dominated by genetic testing and targeted therapy. Although NEN incidence is growing, treatment selection and prognosis prediction rely on clinicopathological factors (staging, grading, differentiation), lacking precision biomarkers or assays for guiding therapy.

Ultrasound, CT, and MRI—common imaging modalities—struggle to accurately diagnose and assess NEN. Thus, a highly sensitive diagnostic tool is urgently needed to address clinical demands.

Nuclear medicine plays a fundamental role in NEN diagnosis and research, particularly in somatostatin receptor (SSTR) imaging. As most NEN express SSTR, SSTR analogs serve as targets for radionuclide imaging [3].  $^{111}\text{In}$ -DTPA-D-Phe1-octreotide (Octreoscan) SPECT is a classic method for diagnosing SSTR-positive NEN [4]. However, ( $^{68}\text{Ga}$ )-labeled DOTA-SSTR PET/CT (e.g., DOTA-Tyr( $^3$ )-octreotate [DOTATATE], DOTA-Nal( $^3$ )-octreotide [DOTA-NOC], DOTA-Tyr( $^3$ )-octreotide [DOTATOC]) reduces scan time, enhances spatial resolution, detects more lesions [5]. Different  $^{68}\text{Ga}$ -DOTA-SSTR tracers exhibit subtype-specific affinity:  $^{68}\text{Ga}$ -DOTATATE targets SSTR2;  $^{68}\text{Ga}$ -DOTA-NOC prefers SSTR3/SSTR5;  $^{68}\text{Ga}$ -DOTATOC has lower SSTR5 affinity [6]. Recent studies [7–11] confirm  $^{68}\text{Ga}$ -DOTA-SSTR PET/CT's high diagnostic value for localizing primaries, guiding clinical strategy, detecting occult metastases, and improving staging/prognosis. Thus, Nordic/U.S. guidelines endorse SSTR PET/CT for NEN diagnosis.

$^{18}\text{F}$  (97%  $\beta(+)$ ,  $T_{1/2} = 109.7$  min) is ideal for peptide-based PET imaging due to favorable physicochemical properties [12].  $^{18}\text{F}$ -FDG, the most common PET tracer, is preferred for aggressive/poorly differentiated NEN but lacks sensitivity/specification for indolent/well-differentiated cases [13–14]. Compared to  $^{68}\text{Ga}$  tracers,  $^{18}\text{F}$ -labeled SSTR offers superior resolution potential, making it clinically valuable.

$^{18}\text{F}$ -AlF-NOTA-octreotide ( $^{18}\text{F}$ -Octreotide) enables rapid peptide synthesis, accumulates markedly in NEN, and exhibits excellent safety/dosimetry. Versus  $^{18}\text{F}$ -FDG,  $^{18}\text{F}$ -Octreotide provides better tumor-to-background contrast in well-differentiated NEN imaging [15].

## 2. Research Objectives and Content

### 2.1 Objectives

This study utilizes 18F-Octreotide PET/CT or PET-MR in suspected/confirmed NEN patients to evaluate diagnostic efficacy (via postoperative pathology), therapeutic response, and prognosis prediction. It aims to clarify the role of 18F-Octreotide imaging in tumor localization, treatment planning, prognosis, and peptide receptor radionuclide therapy (PRRT) selection. The technique also holds promise for lesion segmentation, grading, survival prediction, and genotyping.

## 2.2 Research Content

- (1) Primary diagnosis cohort: Multimodal imaging 18F-Octreotide PET/CT or PET-MR + contrast-enhanced CT/MR) followed by biopsy/surgical pathology (gold standard, including grading, Ki-67, SSTR2, TP53/Rb status).
  - (a) Diagnostic efficacy: Calculate sensitivity, specificity, NPV, PPV, AUC-ROC; assess concordance between imaging and pathology.
  - (b) TNM staging: Compare lesion detection rates of 18F-Octreotide imaging vs. CT/MR; evaluate staging accuracy.
  - (c) Tumor heterogeneity: Quantify intratumoral heterogeneity via 18F-Octreotide PET; develop quantitative methods and compare with radiomics for predicting pathological complete response (pCR).
- (2) Recurrence cohort: Post-treatment (surgery/endocrine therapy/chemotherapy) multimodal imaging.

Assess response per PERCIST criteria, explore dynamic imaging parameters for recurrence risk prediction.

Combine radiomics/AI to identify prognostic parameters.

## 3. Tracer Characteristics, Mechanism, and Scope

### 3.2 Tracer Characteristics

Quality control per Chinese Pharmacopoeia (2015 edition), Radiopharmaceutical Testing:

Appearance: Colorless, transparent, sterile, pyrogen-free aqueous/ethanol (15%) solution.

pH: Within specified range (tested via pH strip/meter).

Specific activity:  $\geq 37 \times 10(^3)$  MBq/mol (measured by activimeter).

Radionuclide purity:  $\gamma$ -spectrometry shows only 0.511 MeV and 1.02 MeV peaks.

Radiochemical purity:  $\geq 95\%$  (TLC/HPLC).

Chemical purity:  $\geq 95\%$  (HPLC).

Microbiology: Sterile, apyrogenic.

Endotoxin: Below threshold.

Acetonitrile:  $\leq 0.01\%$

K222:  $\leq 50$  ng/mL.

### 3.3 Mechanism and Scope

$^{18}\text{F}$ 's properties make it ideal for peptide-based PET [12]. While  $^{18}\text{F}$ -FDG suits aggressive NEN, it underperforms in indolent cases [13–14].  $^{18}\text{F}$ -labeled SSTR tracers offer higher resolution than  $^{68}\text{Ga}$  analogs, promising broad clinical utility.

## 4. Indications, Contraindications, and Precautions

4.1 Indications: Suspected or confirmed NEN patients.

4.2 Contraindications:

Inability to undergo biopsy/surgery.

Active malignancy or history within 5 years.

Severe uncontrolled comorbidities/active infections.

Inability to provide informed consent.

#### 4.3 Precautions:

Pregnant/lactating women require medical guidance and signed consent.

### 5. Overall Design

#### 5.1 Research Methodology

This prospective, single-center, cross-sectional study evaluates the diagnostic efficacy of 18F-Octreotide PET/CT in patients with neuroendocrine neoplasms (NEN). A total of 152 subjects will be enrolled from the First Affiliated Hospital, Zhejiang University School of Medicine.

#### 5.2 Bias Minimization Measures

5.2.1 Blinding: Not applicable (open-label).

5.2.2 Clinical Endpoint Determination: Biopsy or surgical pathology serves as the gold standard.

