## 6.3 Medical History Collection

Comprehensive documentation of:

- Symptoms, signs, and history (tumors, surgeries, biopsies, radiotherapy, chemotherapy, allergies, octreotide/PRRT history).
- Lab tests: Fasting insulin, CgA, proinsulin/C-peptide, NSE, VIP, Syn, VMAT-2, CD56.
- Prior imaging (X-ray, US, CT, MRI, 18F-FDG PET/CT/MR).
- Recent pathology (grading, Ki-67 index).

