## 6.7 Image Interpretation

- Normal Biodistribution: Spleen (highest), kidneys, liver, adrenals, pituitary, salivary glands. Minimal uptake in brain/lungs/muscle; excreted via kidneys.
- Pathologic Uptake: Focal uptake in non-physiologic sites (vs. diffuse bowel uptake = non-pathologic).
- Malignancy Criteria: Uptake  $>$  liver = SSTR-positive malignancy. Correlates with tumor grade/SSTR expression.

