## 6.8 Reporting Standards

Objectives: Address referring physicians' clinical queries and justify necessity/diagnostic value of  $\text{^{18}F}$ -Octreotide imaging.

Procedure Flow:

Registration → 2. Preparation (fast  $\geq 4$ h) → 3. History/consent → 4.  $\text{^{18}F}$ -Octreotide injection → 5. Uptake period (60 min) → 6. Scan (20–30 min).

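### Protocol section 5.2.1 rules out blinding because the study is open-label, so PET reads are not protected from knowledge of the pathology or the comparator CT/MR

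*Protocol*

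**What the plan says.** Section 5.2 (Bias Minimization Measures) deals with blinding in one line: "5.2.1 Blinding: Not applicable (open-label"). The other sections that bear on the point are these.

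- **Who is evaluated.** Section 2.1 applies the tracer "in suspected/confirmed NEN patients to evaluate diagnostic efficacy (via postoperative pathology"). Section 4 repeats the population: "4.1 Indications: Suspected or confirmed NEN patients".
- **What is known beforehand.** Section 6.3 collects "Recent pathology (grading, Ki-67 index") in the medical history, together with prior CT, MRI and FDG PET.
- **Order of tests.** In the primary diagnosis cohort of section 2.2, imaging is "followed by biopsy/surgical pathology (gold standard, including grading, Ki-67, SSTR2, TP53/Rb status").
- **Comparator.** For the same cohort, section 2.2 plans to "Compare lesion detection rates of 18F-Octreotide imaging vs. CT/MR; evaluate staging accuracy".
- **Reading.** Section 8.1 has two nuclear medicine physicians read independently, with a senior consultant settling disagreements. Section 6.7 calls uptake above liver malignant and describes pathologic uptake as "Focal uptake in non-physiologic sites (vs. diffuse bowel uptake = non-pathologic").
- **Analysis.** Section 7.3 derives sensitivity, specificity, predictive values and kappa from PET against pathology.

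**The concern.** The stated reason does not support the rule. Whether a study is open-label concerns knowledge of treatment. An accuracy study needs the index test to be read without knowledge of the reference standard, and a modality comparison needs each modality to be read without the other. By declaring blinding inapplicable, the protocol makes a decision on this point rather than leaving it open.

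A reader who knows that a patient has NEN can resolve equivocal uptake towards NEN, which raises sensitivity and kappa. Specificity can rise as well, but mainly if reads are made or revised after pathology has returned. The detection comparison can be distorted if PET is read with the CT/MR in hand, or the reverse; the direction depends on who sees what. This is bias rather than sampling error, so more patients would not reduce it and the confidence interval would not reveal it.

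**Working it through.** **1. Can readers know the pathology?**

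- Section 2.1 puts confirmed patients into the efficacy evaluation, and section 6.3 collects recent pathology. Some patients may therefore have a relevant result on file before the scan.
- In the primary diagnosis cohort, imaging comes before the study pathology (section 2.2). No section fixes when the formal read is made or locks it before pathology arrives.
- Section 8.1 makes the two readers independent of each other, not of the pathology or the CT/MR. The adjudicator, who decides the difficult cases, is not masked either.
- The liver threshold in section 6.7 is partly objective, but deciding whether a focus is physiologic remains a judgement.

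Access is therefore plausible, and nothing prevents it.

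**2. The plan's own figures (section 7.1).** Inputs: sensitivity 0.90, specificity 0.88, prevalence 0.25, margin 0.10.

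- N1 = 1.96² × 0.90 × 0.10 / (0.10² × 0.25) = 138.3, stated as 138.
- N2 = 1.96² × 0.88 × 0.12 / (0.10² × 0.75) = 54.1, stated as 54.
- 138 × 1.10 = 151.8, stated as 152.

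These figures reproduce, and masking does not change them.

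**3. Expected table at N = 138**

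| | NEN | Not NEN |
|---|---|---|
| PET positive | 31.05 | 12.42 |
| PET negative | 3.45 | 91.08 |
| Total | 34.5 | 103.5 |

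Observed agreement = (31.05 + 91.08)/138 = 0.885. Chance agreement = (43.47 × 34.5 + 94.53 × 103.5)/138² = 0.5925. Kappa = (0.885 − 0.5925)/(1 − 0.5925) = 0.718.

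**4. Effect of single reads**

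| Change | Result | Shift | Share of 0.10 margin | Kappa |
|---|---|---|---|---|
| One miss re-read as positive | sensitivity 0.929 | 1/34.5 = 0.029 | 29% | 0.738 |
| Two misses re-read as positive | sensitivity 0.958 | 2/34.5 = 0.058 | 58% | 0.758 |
| One false positive reversed | specificity 0.890 | 1/103.5 = 0.010 | 10% | not calculated |

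**5. Other NEN shares (assumption).** Including confirmed patients may push the NEN share above 0.25. At 0.50 there are 69 NEN patients, and one reversed miss adds 1/69 = 0.014. At 0.75 there are 103.5, and it adds 0.010. Expected misses then rise to 6.9 and 10.35, so each read counts for less but more reads are open to revision. If a fixed share f of misses is reversed, sensitivity rises by 0.10 × f whatever the NEN share: 0.010, 0.025 or 0.050 for f = 10%, 25% or 50%. These values of f are assumptions; the protocol gives no basis for choosing one.

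**The case against.** The strongest reply is that exposure to the study reference result is narrow. Diagnostic efficacy belongs to the primary diagnosis cohort in section 2.2, where imaging comes first. For patients treated elsewhere, pathology arrives later by telephone. The recurrence cohort, where earlier pathology is most likely, is given response and prognosis aims. The inclusion criteria in section 5.3.1 speak of clinically diagnosed or suspected disease and do not mention pathological confirmation, and section 6.3 describes what is recorded, not what readers are shown. This limits the problem: a prompt read in a patient without earlier pathology cannot be influenced by it. The gap stays open because the protocol does not require a prompt or locked read, section 2.1 includes confirmed patients, and section 5.2.1 rules out the safeguard.

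It can also be said that the liver threshold and the SUV-based ROC analysis leave less room for expectation. That is fair for the quantitative analysis, although choosing which focus to measure is still a judgement.

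On CT/MR, the protocol does not say who reads it or in what order, and such detail often sits in a reading manual or SAP. That part is therefore secondary. It still falls under the blanket statement in section 5.2.1, which treats no blinding as applicable.

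Finally, the arithmetic shows leverage and does not demonstrate bias; any study of this size would show the same effect per read. That is correct, and the figures should be read only as illustration.

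**Conclusion.** The concern holds and should be fixed. Section 5.2.1 states a mistaken rule, and as written the accuracy estimates cannot be shown to be independent of the reference standard. The protocol gives neither the share of patients with earlier pathology nor the timing of reads, so whether bias will occur, and how large it would be, cannot be derived. What can be said is that about 3.5 expected misses carry the sensitivity estimate. Under the planning inputs, reversing one moves it by 0.029 and kappa from 0.72 to 0.74; reversing two moves it by 0.058 and kappa to 0.76. At assumed NEN shares of 0.50 and 0.75 the shift per read falls to 0.014 and 0.010. The planned sample size is unaffected.

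**What to change.** Replace section 5.2.1 with wording such as:

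> For the diagnostic accuracy and lesion-detection analyses, the two planned readers and the adjudicating consultant score de-identified 18F-Octreotide PET/CT or PET/MR, including its hybrid CT or MR component, blinded to pathology and to the separate contrast-enhanced CT/MR and its report. The patient-level result is locked before pathology is released to them. The contrast-enhanced CT/MR is scored without the PET result. Response assessment in the recurrence cohort may use earlier scans, and the clinical report may use all information.

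The PET part uses the readers already named in section 8.1 and needs de-identified read lists and a lock step. Scoring CT/MR without PET needs separate sessions or separate readers. If that is not feasible, masking to pathology and the lock are worth having on their own. A small downside is that the research read may differ from the fully informed clinical read and may be an additional read. The rule has to be in place before reading begins, because a reader who has seen the pathology cannot afterwards be blinded for that patient.
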